**CLOSED Aim 3: To determine if the adaptive increase in  $\beta_2$ -nAChR availability and change in  $\beta_2$ -nAChR availability over the first month of abstinence in smokers is genetically predisposed.** We will determine if ANKK1 or CHRNA4 genotypes are associated with changes in  $\beta_2$ -nAChR availability in smokers over time recruited in aim 2. The same smokers from Aim 2 will be supported to maintain abstinence for 4-8 weeks. Smokers that successfully abstain for 4-8 weeks (~ 50%; e.g. 5 smokers) will be imaged a second time using NCFHEB and PET. The % change in  $\beta_2$ -nAChR availability will be determined as the difference in NCFHEB binding  $[(V_T/f_p @7\text{days of abstinence} - V_T/f_p @4\text{ wks abstinence})/V_T/f_p @7\text{ days abstinence}]$ . Blood samples for DNA extraction will be collected from all subjects.

**Hypothesis:** Based on our preliminary data we hypothesize that smokers that carry the A allele for hCV16178933/rs2273504 or the G allele for hCV15953820/rs2236196 genotype will have higher  $\beta_2$ -nAChR availability at 7-9 days of abstinence compared to never smokers matched for age and sex and genotype. Whereas smoker homozygotes (GG and AA respectively for hCV16178933/rs2273504 or for hCV15953820/rs2236196) will demonstrate similar  $\beta_2$ -nAChR availability compared to never smokers. We also hypothesize that CC homozygotes for the CHRNA4 rs2273502 will show a pronounced decrease in  $\beta_2$ -nAChR availability while carriers of the T allele show no change in  $\beta_2$ -nAChR availability will demonstrate the greatest change or normalization over 6 weeks of abstinence.

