### 3.7 Statistical analysis.

**3.7 a Power Analysis in Never Smokers:** Assuming Hardy-Weinberg equilibrium, the allele frequency predicts that 30 will be homozygous (CC); 25 will be heterozygous (CT) and 5 will be homozygous (TT) for the ANKK1 alleles, and 11 will be homozygous (AA) 29 will be heterozygous (AG) and 20 will be homozygous (GG) for the CHRNA5 alleles. In a one-way ANOVA analysis, sample sizes of 30, 25, and 5 are obtained from the three genotypes of ANKK1 whose means are to be compared. The total sample of 30 subjects achieves 0.96 power to detect differences among the means versus the alternative of equal means using an F test with a 0.05 significance level for thalamus. The size of the variation in the means is represented by their standard deviation which is 17.49. The common standard deviation within a group is assumed to be 32.30. The other powers are 0.95, 0.87, and 0.99 for ANKK1 for the brain regions of striatum, cerebellum and cortex, respectively. We have enough power to detect the effect with the proposed sample size. We aim to recruit at least 10 subjects that are homozygous for TT; if we do not achieve our goals for the rarer genotype by the end of year 3; we will screen subjects prior to imaging them in year 4.

**3.7.b Power Analysis in Smokers:** The group means of  $\alpha_2$ -nAChR availability for the heterozygotes of hCV16178933/rs2273504 or hCV15953820/rs2236196 are higher in smokers than non-smokers in the brain regions of striatum, cerebellum and mean cortex, but not thalamus. We can achieve 0.81 power to detect a difference of 11.7 in striatum between the null hypothesis that both group means are 97.5 and the alternative hypothesis that the mean of non-smoking group is 85.8 with estimated group standard deviations of 14.9 and 10.8 and with a significance level (alpha) of 0.05000 using a one-sided two-sample t-test for hCV16178933/rs2273504. The other powers are 0.97, 0.95 for hCV16178933/rs2273504 and for cerebellum and mean cortex, respectively. The differences do not present in the homozygote subjects. We can also achieve 0.98 to 0.99 for hCV15953820/rs2236196 in the brain regions of striatum, cerebellum and mean cortex.

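### Aim 3 claims that CHRNA4 genotype modifies the smoking effect, but the only test and power given are for heterozygotes alone, and 10 + 10 subjects cannot reach the stated 0.81

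*Combined protocol and SAP*

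**What the plan says.** The combined document holds two protocols; this point concerns the NCFHEB one. In Section II, item 1, the Aim 3 hypothesis says that "smokers that carry the A allele for hCV16178933/rs2273504 or the G allele for hCV15953820/rs2236196 genotype will have higher" receptor availability at 7-9 days of abstinence than matched never smokers. It continues: "Whereas smoker homozygotes (GG and AA respectively for hCV16178933/rs2273504 or for hCV15953820/rs2236196) will demonstrate similar" availability to never smokers.

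Section 3.7.b (Power Analysis in Smokers), repeated under item 12 (Statistical Considerations, Smokers), gives the statistical support: "We can achieve 0.81 power to detect a difference of 11.7 in striatum". The calculation contrasts a smoker mean of 97.5 with a non-smoker mean of 85.8, takes SDs of 14.9 and 10.8, sets alpha at 0.05, and is done "using a one-sided two-sample t-test for hCV16178933/rs2273504". For the same SNP it gives powers of 0.97 (cerebellum) and 0.95 (mean cortex), and for rs2236196 0.98 to 0.99. It adds: "The differences do not present in the homozygote subjects". No group sizes accompany these powers.

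Aim 2 supplies the subjects: 10 never smokers and 10 smokers, all genotypes together. Aims 2 and 3 are both marked CLOSED, and the Background describes their SNP work as exploring relationships.

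The last sentence of the Aim 3 hypothesis, on rs2273502, first says that T carriers show no change and then that they "will demonstrate the greatest change or normalization over 6 weeks of abstinence".

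**The concern.** Carriers upregulate and the other homozygotes do not: that is a statement about a difference between two differences. A test inside heterozygotes asks only whether smoking matters there. A significant result in one stratum beside a non-significant one in another does not show that the strata differ, and a non-significant homozygote comparison does not show similarity.

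Two things are at stake. A report could claim genetic predisposition where smoking acts alike in every genotype. And the genetic question is credited with 0.81 power that belongs to another question and a larger sample.

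**Working it through.** **Inputs.** Difference 11.7 (97.5 v 85.8), SDs 14.9 and 10.8, one-sided alpha 0.05 (Section 3.7.b); 10 smokers and 10 never smokers (Aim 2). The number of homozygotes is not stated and is varied below.

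**1. The 0.81.** With n per group, SE = sqrt((14.9² + 10.8²)/n) = sqrt(338.65/n). Power is from the noncentral t with unequal variances.

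| n per group | SE | 11.7/SE | one-sided power |
|---|---|---|---|
| 5 | 8.23 | 1.42 | 0.36 |
| 10 | 5.82 | 2.01 | 0.61 |
| 16 | 4.60 | 2.54 | 0.798 |
| 17 | 4.46 | 2.62 | 0.820 |

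So 0.81 implies 16-17 heterozygotes per group if groups are equal. With 10 per group, power is 0.61 even if every subject were heterozygous.

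**2. Power for the claim.** The contrast is the smoker difference in heterozygotes minus that in homozygotes. With equal cells its SE is sqrt(2) times the SE above. The true value is taken as 11.7 - 0 = 11.7, with the same SDs.

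| n per cell | SE | 11.7/SE | two-sided | one-sided |
|---|---|---|---|---|
| 5 (the planned 10 + 10, split evenly) | 11.64 | 1.01 | 0.16 | 0.25 |
| 17 | 6.31 | 1.85 | 0.45 | 0.57 |

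Power of 0.81 would need about 32 per cell one-sided (4 × 32 = 128 subjects) or 41 two-sided (4 × 41 = 164), against 20 planned.

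**3. How often the pattern arises with no modification.** With one true smoking effect in both strata and independent strata, P(heterozygotes significant, homozygotes not) = p_het × (1 - p_hom), where p is the one-sided power in each stratum.

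| Assumption | p_het × (1 - p_hom) | Rate |
|---|---|---|
| Both strata at the stated 0.81 | 0.81 × 0.19 | 15% |
| Both at 0.5 (the maximum for equal power) | 0.5 × 0.5 | 25% |
| 10 + 10 split 5/5, difference 11.7 | 0.361 × 0.639 | 23% |
| 10 per group, 3 heterozygotes and 7 homozygotes | 0.230 × 0.527 | 12% |
| 10 per group, 7 heterozygotes and 3 homozygotes | 0.473 × 0.770 | 36% |
| 17 heterozygotes and 10 homozygotes per group | 0.820 × 0.389 | 32% |
| 17 heterozygotes and 5 homozygotes per group | 0.820 × 0.639 | 52% |
| Both at 0.95 | 0.95 × 0.05 | 4.8% |
| Both at 0.99 | 0.99 × 0.01 | 1.0% |
| No smoking effect | 0.05 × 0.95 | 4.8% |

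Simulation (50,000 runs each) gave 14.9% at 17 per cell and 22.9% at 5 per cell.

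**4. Wording.** The hypothesis speaks of allele carriers, which for rs2273504 means AG and AA; the power text speaks of heterozygotes only. For rs2273502, the same sentence gives T carriers no change and the greatest change. The Background (chronic nicotine exposure) reports that some smokers fall by 14-17% and others change by less than 4%, and links this to rs2273502, without saying which genotype does which.

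**The case against.** The homozygote remark stands in a power paragraph, in the present tense, and the hypothesis is introduced as based on preliminary data. Nowhere do the documents say that a non-significant homozygote test will be the rule for inferring modification. A reader might infer such a rule, but the text does not support it. This objection stands. What remains is that the claim has no analysis of its own, and the one test described does not address it.

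A reader might also take 15-25% as the general false-claim rate of the plan. It is not. It needs a real, common smoking effect and equal, moderate power in both strata, and 0.81 is the lowest of the stated smoker powers. At the other stated powers, if equal in both strata, the rate is about 1-5%.

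A third tempting reading is that the rs2273502 hypothesis could never be contradicted. The sentence is garbled, but it opens with a plain contrast (CC decreases, T carriers do not) and the Background supports a contrast of that kind. It is an editing error.

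Finally, the aims are closed and exploratory, and 20 subjects can barely inform an interaction model. Both points stand and reduce the weight of the concern. They do not remove it, because item 12 still carries these powers and the data may still be analysed or reported.

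**Conclusion.** The concern holds in a limited form. The Aim 3 genetic claim is an interaction for which the NCFHEB protocol gives no test, no power and no margin or interval for similarity. The stated 0.81 is heterozygote-only power at an implied 16-17 per group. For the planned 10 + 10 it is at most 0.61, and two-sided interaction power is about 0.16 on an even split.

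The chance of seeing the expected pattern without any modification depends on homozygote numbers that are not given: about 15-25% under equal, moderate power (23% for the even 5/5 split), about 1-5% at power 0.95-0.99 or with no smoking effect, and 30-50% if homozygotes are much fewer. These rates assume the plan's SDs in both strata and, except in the no-effect case, a common smoking effect. The defect itself depends on none of them. Because the aims are closed and exploratory, this is a correction to make before analysis or reporting.

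**What to change.** For any analysis or report of these aims:

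- Base the genetic claim on the two-sided smoking-by-genotype estimate and its confidence interval.
- Report the homozygote smoker difference with its interval, in place of a statement of similarity.
- Restate 0.81 as heterozygote-only power at its implied n, and give beside it the power for 10 + 10 and for the interaction.
- Label the result exploratory.
- Reconcile carriers (Aim 3) with heterozygotes (Section 3.7.b and item 12).
- Correct the rs2273502 sentence to one direction for T carriers.

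This costs wording and one model, with no new subjects or scans. The downside is that the stated power becomes much less favourable and the interaction estimate will be imprecise.

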**CLOSED Aim 7. To determine amphetamine-induced DA release in tobacco smokers during acute withdrawal and in nonsmokers.** Smoker and nonsmoker subjects from Aim 4 will participate. Each subject will participate in up to 2 [ $^{11}\text{C}$ ]PHNO PET scans (ideally, the two PET scans will be carried out in the same day). Up to three hours before the second PET scan, amphetamine (0.5 mg/kg, PO) will be administered. In smokers, the scan will occur at 10-30 days of smoking abstinence. We hypothesize that at 10-30 days of withdrawal amphetamine-induced DA release will be blunted compared to healthy nonsmokers.

**CLOSED Aim 8. To determine the degree of occupancy of the  $\beta_2^*$ -nAChRs by nicotine after use of an e-cig compared to a tobacco cigarette using [ $^{18}\text{F}$ ]NCFHEB PET neuroimaging.** Given recent evidence that experienced e-cig users can achieve similar plasma nicotine levels compared to tobacco smoking, we hypothesize there will not be a significant difference in  $\beta_2^*$ -nAChR occupancy by nicotine after use of an e-cig as compared to a regular cigarette. We will also examine arterial plasma nicotine levels and compare to nicotine occupancy of the nAChRs between groups.

2. **Background:** Describe the background information that led to the plan for this project. Provide references to support the expectation of obtaining useful scientific data.

The cholinergic system, and the beta2-nicotinic acetylcholine receptors ( $\beta_2$ -nAChRs) specifically, have been implicated in many neuropsychiatric conditions, such as addiction, depression, schizophrenia and AD.(3-6) This involvement has been supported by molecular imaging studies of the  $\beta_2$ -nAChR, including studies performed by our group at Yale.(7-13) The  $\beta_2$ -nAChRs are the most abundant nAChRs in the brain. Until very recently,  $\beta_2$ -nAChR SPECT and PET radiotracers available for human use displayed slow kinetics, requiring prolonged scanning sessions(14, 15), and practically eliminated our ability to study severely impaired patients.(16, 17) The recently introduced radiolabeled antagonist (-)-2-(6-(18)F-fluoro-2,3'-bipyridin-5'-yl)-7-methyl-7-azabicyclo[2.2.1]heptane ([ $^{18}\text{F}$ ]NCFHEB or NCFHEB) has been

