Receptor imaging has been successfully utilized to examine mechanisms of tobacco addiction through evaluation of  $\beta_2^*$ -nAChR availability as a consequence of tobacco smoking

 as well as occupancy by nicotine in multiple previous studies. Findings suggest that typical smokers maintain near complete receptor occupancy throughout the day, and that lower receptor occupancy levels lead to craving. As an example of our work, we compared  $\beta_2^*$ -nAChR occupancy between the Nicotrol nicotine inhaler and a regular tobacco cigarette using [I]5-IA and SPECT imaging. We determined that using the inhaler leads to an average  $55.9 \pm 6.4\%$  occupancy by nicotine of the  $\beta_2^*$ -nAChRs, which was significantly less compared to the  $67.6 \pm 14.1\%$  occupancy after use of a tobacco cigarette. Further, we detected that arterial plasma nicotine concentration was significantly lower after use of the inhaler as compared to a regular cigarette. We observed a significant reduction in withdrawal but not craving symptoms associated with the use of the inhaler. These findings suggest that the nicotine occupancy after use of the inhaler may be at the degree of attenuating nicotine withdrawal; however, greater saturation of the receptors may be required to relieve nicotine craving symptoms. These data also suggest the nicotine inhaler has lower potential for abuse and addiction compared to a regular cigarette.

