**Aim 6: To determine the efficacy of a bolus to infusion scan versus a bolus scan of NCFHEB with physostigmine challenge.**

**CLOSED Aim 7: To determine amphetamine-induced DA release in tobacco smokers during acute withdrawal and in nonsmokers with [ $^{11}\text{C}$ ] PHNO.**

**CLOSED Aim 8. To determine the degree of occupancy of the  $\beta_2^*$ -nAChRs by nicotine after use of an e-cig compared to a tobacco cigarette using [ $^{18}\text{F}$ ]NCFHEB PET neuroimaging in 10 subjects.**

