### **Cigarette challenges (same procedures as in protocol HIC 0804003655)**

Subjects will participate in one or more PET scans during which they will participate in 4 possible smoking challenges: Smoking an e-cig with no nicotine, an e-cig with a low dose of nicotine (6mg/mL-10mg/mL), an e-cig with a high dose of nicotine (24 mg/mL-36mg/mL), or smoking a regular cigarette. Subjects will participate in a different challenge for each of their PET scans. For the e-cig challenges, subjects will not be aware of the amount of nicotine in the e-cig. Subjects will abstain from smoking for ~1 week prior to each challenge day. After each PET scan, subjects will return to smoking for at least 1 week. They will then need to abstain from smoking for ~1 week prior to participating in their next PET scan. Because of this off-and-on smoking cessation, only non-treatment-seeking smokers will be asked to participate in this study. We have employed this procedure previously for protocol HIC 0804003655.

Use of e-cig: Based on the findings of a recent study that showed use of e-cigs led to similar plasma nicotine levels as tobacco smoking within 5 minutes of use, we plan to use an e-Go type e-cig battery (3.3 V, 1000 mAh) with 1.5 ohm dual-coil 510-style cartomizer and a 70/30 propylene glycol vegetable glycerin e-liquid with nicotine concentrations of approximately 0mg/mL, 6mg/mL-10mg/mL, and 24mg/mL-36mg/mL. Subjects will be instructed to puff on the e-cig once every 30 seconds in a manner as they normally would puff on a cigarette for 10 puffs total. A mouthpiece to measure puff topography may be used.

Use of regular cigarette: To standardize research methodology, Camels brand cigarettes will be used for all subjects. This brand is not prevalent with the smokers who participate in our studies and any subject who has used this brand prior will be excluded. Subjects will be instructed to

puff every 30 sec for a total of 10 puffs via the puff device (CreSS from Plowshare Technologies, USA), which provides measures of depth of puff inhalation and volume.

Blood Samples: On PET scan days, blood samples will be collected prior to radiotracer administration and at multiple time points after e-cig and tobacco cigarette use to determine nicotine concentrations in the blood, which will be assayed using reversed-phase HPLC .

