**CLOSED** Aim 8. Subjects who previously participated in Aim 4 or 6, or new subjects may complete this portion of the protocol as long as their yearly radiation dose allows. For Aim 8, subjects will participate in one or more PET scans during which they will participate in 4 possible smoking challenges: Smoking an e-cig with no nicotine, an e-cig with a low dose of nicotine (6mg/mL-10mg/mL), an e-cig with a high dose of nicotine (24 mg/mL-36mg/mL, or smoking a regular cigarette. Subjects will participate in a different challenge for each of their PET scans.. For each scan, up to 8mCi of NCFHEB will be administered as a bolus plus constant infusion for the duration of the scan (up to 4 hours). Once equilibrium is reached (approximately two hours into the scan), subjects will use a cigarette or e-cigarette (order will be predetermined ahead of time and subjects will be told what they will be using for each scan. However, if subjects are using the e-cig they will not be told which nicotine concentration they will receive). A transmission scan will be acquired.

Control subjects may participate in more than 1 aim. For example, nonsmoking subjects may complete Aim 1 and if they choose, participate in Aim 4. Thus, subjects may participate in up to 4 NCFHEB PET scans and up to 2 PHNO PET scans for this protocol per year. Subjects who complete 4 NCFHEB and 2 PHNO scans may return after 365 days to complete more scans under additional aims in this protocol.

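### Aim 8 predicts no significant occupancy difference in 10 subjects with no margin, analysis rule or named e-cigarette concentration, so its only stated criterion is one that an imprecise study tends to meet

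*Combined protocol and SAP*

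**What the plan says.** The point concerns the NCFHEB protocol, the first of the two in the combined document.

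- **Hypothesis.** Section II, 1. Statement of Purpose, Aim 8: "we hypothesize there will not be a significant difference in" receptor occupancy by nicotine after an e-cigarette compared with a regular cigarette. The aim is marked closed.
- **Sample size.** Section 3.1, Overall plan, sets the aim as "NCFHEB PET neuroimaging in 10 subjects", with no justification of that number.
- **Design.** Section 3.5, under PET, Aim 8: "subjects will participate in one or more PET scans during which they will participate in 4 possible smoking challenges". The four are an e-cigarette with no nicotine, one with a low dose, one with a high dose, and a regular cigarette. Under Cigarette challenges: "Subjects will participate in a different challenge for each of their PET scans". The hypothesis does not say which e-cigarette condition is set against the cigarette.
- **Analysis.** Sections 3.7 (Statistical analysis) and 12 (Statistical Considerations) cover genotype comparisons only. They give no test, alpha, margin, interval rule or power for Aim 8.
- **The group's own comparator.** Section 2, Background, E-cigarettes, reports occupancy by 5-IA SPECT of 55.9 ± 6.4% after a nicotine inhaler, "which was significantly less compared to the" 67.6 ± 14.1% after a cigarette. A few lines later: "These data also suggest the nicotine inhaler has lower potential for abuse and addiction compared to a regular cigarette".

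**The concern.** A hypothesis of no significant difference agrees with any non-significant test. Small numbers and noisy measurements make non-significance more likely, so imprecision works in the hypothesis's favour. With no margin, the protocol does not say how large a difference would still count as similar. With no interval rule, nothing obliges the analyst to show which differences the data exclude.

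The Background shows why this matters. In a neighbouring comparison the group reported a gap of 11.7 occupancy points as significant, and used it as part of an argument about abuse potential. If Aim 8 could return a non-significant result while a gap of that size was real, that result would not be good evidence that the two products occupy the receptors alike.

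**Working it through.** The documents state no power, detectable difference or margin for Aim 8, so there is no figure to reproduce. The calculation below is an illustration.

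**Inputs from the documents** (Background, E-cigarettes; Section 3.1)
- Gap: 67.6 − 55.9 = 11.7 points.
- Spreads: 6.4 (inhaler) and 14.1 (cigarette).
- n = 10.

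**Assumptions**
- ± is an SD; the document does not label it.
- The inhaler's SD applies to e-cigarettes.
- Alpha is two-sided 0.05.
- The within-person correlation ρ is not given; 0 to 0.7 is used.
- The analysis is a paired t-test on complete e-cigarette/cigarette pairs.

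**Formulas**
- SD of the difference = √(6.4² + 14.1² − 2ρ × 6.4 × 14.1) = √(239.77 − 180.48ρ).
- 95% CI half-width with 10 pairs = 2.262 × SD / √10.
- Power: noncentral t with n − 1 df and noncentrality 11.7 / (SD / √n). Miss rate = 1 − power.

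**Worked case, ρ = 0.5, 10 pairs.** SD = √(239.77 − 90.24) = √149.53 = 12.23. Standard error = 12.23 / √10 = 3.87. Half-width = 2.262 × 3.87, about 8.7 points. Noncentrality = 11.7 / 3.87 = 3.02. Power is 77% and the miss rate 23%.

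| ρ | SD of difference | 95% half-width, 10 pairs | Power, 10 pairs | Miss, 10 pairs | Power, 8 pairs | Miss, 8 pairs |
|---|---|---|---|---|---|---|
| 0 | 15.48 | 11.1 | 57% | 43% | 45% | 55% |
| 0.25 | 13.95 | 10.0 | 66% | 34% | 53% | 47% |
| 0.5 | 12.23 | 8.7 | 77% | 23% | 64% | 36% |
| 0.7 | 10.65 | 7.6 | 87% | 13% | 76% | 24% |

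**What a non-significant result could look like.** Suppose the observed difference were 6 points. At ρ = 0 the 95% CI is 6 ± 11.1, or −5.1 to 17.1. At ρ = 0.7 it is 6 ± 7.6, or −1.6 to 13.6. Both are non-significant and both include 11.7. An observed difference near zero would behave differently, because every half-width in the table is below 11.7.

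**Sensitivity to the SDs, 10 pairs.** If both conditions had SD 14.1, power is 38% at ρ = 0 and 65% at ρ = 0.5. If both had SD 6.4, it is at least 95%.

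**Showing similarity instead.** Take two one-sided 5% tests with limits of ±11.7 points and a true difference of zero. Simulated power with 10 pairs is 44%, 58%, 75% and 88% at ρ = 0, 0.25, 0.5 and 0.7. A tighter margin gives less.

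**The case against.** **The plan never says that non-significance will be reported as equality.** A reader might infer from the hypothesis that it would be. No sentence says so; the aim itself is to determine a degree of occupancy, and the hypothesis can be read as a prediction based on plasma nicotine data. This stands, and the point is limited accordingly: no other criterion is written down, so the plan permits the inference without stating it.

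**The chance of a miss depends on assumptions.** A reader might also infer that 10 subjects would easily overlook the gap. The documents do not establish that. With ten full pairs, power passes 80% from a correlation of about 0.55, and smaller SDs would make it ample. Larger SDs or fewer pairs cut the other way, and no correlation or e-cigarette SD is given. The range is illustrative. Adequate power would still not make non-significance evidence of similarity.

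**The benchmark is borrowed.** It is inhaler versus cigarette by 5-IA SPECT, not e-cigarette versus cigarette by NCFHEB PET. The abuse-potential remark also follows plasma nicotine and symptom findings. It remains the nearest occupancy comparison with spreads in the documents, but it is a yardstick only.

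**Regulatory consequence.** The Background ties possible regulation to mechanism, addictive potential and their relation to behaviour, and Aim 8 also compares arterial nicotine. The documents do not rest a regulatory claim on one occupancy p-value.

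**Section 3.7.b quotes 0.81 power for a difference of 11.7 in striatum.** That is a genotype calculation; the matching number is a coincidence and does not support Aim 8.

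**The aim is closed.** This removes any case for more scans. It does not settle how the data are to be analysed and reported.

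**Conclusion.** The point holds in limited form. Non-significance is the only criterion that Aim 8 states, and imprecision favours it. The contrast is also undefined, because there are three e-cigarette conditions and none is named.

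Under the assumptions listed, ten complete pairs would miss an 11.7-point gap in about 43% to 13% of studies as the correlation runs from 0 to 0.7. Ten complete pairs are not assured, since subjects may have as little as one scan. With eight pairs the miss rate is about 55% to 24%. These sizes are conditional on borrowed SDs and an assumed correlation. The defect in the criterion does not depend on them.

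**What to change.** Restate the Aim 8 hypothesis and analysis as estimation:

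1. Name the e-cigarette nicotine concentration that is compared with the cigarette.
2. Report the mean occupancy difference with its 95% CI and the number of complete pairs.
3. Do not conclude similarity from p > 0.05. Claim it only if the 90% CI lies wholly within a margin justified before the analysis and smaller than 11.7 points. A margin of 11.7 itself would let the word similar cover differences almost as large as one the group reported as significant.
4. Otherwise report the result as inconclusive.

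The documents do not say whether the data have been analysed. If they have, a margin set now would not be prespecified, and the estimate with its CI should stand without a similarity claim.

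The cost is wording only, with no new scans. The downside is that the aim may end as inconclusive: with no true difference, ten pairs would meet even an 11.7-point margin in only 44% to 88% of studies, and a smaller margin less often.
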